8.3. Data Analysis Considerations

8.3.1. Analysis Populations

The intent-to-treat (ITT) population will include all randomly assigned subjects. The ITT subjects will be analyzed according to randomised treatment. The inference for primary objectives in the study will be made from ITT population.

Per-protocol Population (PP) will exclude the subjects who have major protocol violations. Per-protocol analysis will include Per-protocol population only and their data upon to the time of discontinuation of investigational product plus 56 days.

The non-insulin population (NI) will include all subjects in the ITT population who are not on insulin at baseline. Inference for the time to insulin endpoint will be made from the NI population.

The baseline basal insulin user population (BI) will include all subjects in the ITT population who are on basal insulin, but not on other insulin at baseline. Inference for the time to prandial insulin endpoint will be made on BI population.

The safety population will include all enrolled subjects who receive at least 1 dose of study treatment. The safety population subjects will be analyzed according to the treatment received. The safety population will be used for analyses of safety objectives.

Other analysis populations will be defined in the RAP.

8.3.2. Analysis Data Set

For time to event data, censoring time for subjects who lost to follow-up is defined as following:

For primary analysis, subjects who are lost to follow-up will be censored at the date of last evidence of confirmatory status for MACE events.

For on-treatment analysis, censoring date will be the last dose date.

For on-therapy analysis (on-treatment+56 days), censoring date will be the last dose date+56 days.

For analysis of all cause of mortality, censoring date will be the latest date known alive.

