The investigational product (albiglutide and albiglutide matching placebo) must be stored in a secure area at 2°C to 8°C and protected from freezing. Each site must maintain a temperature log. Access to and administration of the investigational product will be limited to the investigator and authorised site staff (investigator or designee). Investigational product must be dispensed or administered only to subjects enrolled in the study and in accordance with the protocol.

Procedures for the disposal of unused study treatment will be provided in the SRM.

Investigational product (albiglutide or albiglutide matching placebo) will be administered once weekly by subcutaneous injection. The first dose is to be administered at the clinic. The starting dose of albiglutide will be 30 mg once weekly. If at any stage after 5 weeks of treatment in the opinion of the investigator the subject needs to have intensified therapy to improve glycaemic control, the dose of investigational product should be increased before altering the doses of other glucose-lowering medication. In this case the subject will be called in for an unscheduled visit to supervise an increase in dose from 30 mg to 50 mg. Subjects randomly assigned to albiglutide matching placebo will also go through the increased dose procedure to maintain study blind. If a subject experiences tolerability issues with the higher, 50mg dose then the investigator may decrease the dose back to 30 mg without the need for an unscheduled visit to supervise down titration, other than for the subject to collect pens of the correct dose.

Albiglutide (or albiglutide matching placebo) may be administered at any time of day without regard to meals. Preferably, it should be administered once a week on the same day each week. The day of weekly administration can be changed if necessary as long as the last dose was administered 4 or more days previously. If a dose is missed, it should be administered as soon as possible within 3 days after the missed dose. Thereafter, subjects can resume dosing on their usual day of administration. If it is more than 3 days after the missed dose, subjects should wait and administer their next regularly scheduled weekly dose.

If a subject misses 4 or more consecutive doses, the investigator should contact the medical monitor to discuss options for helping assure better compliance.

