5.5. Treatment Compliance

Subjects will be instructed to return all unused and used injector pens at the visits specified in the Time and Events Table (Table 1) in order to perform drug accountability

and determine compliance. Subjects will be provided with a sharps container for the disposal of used pens. To comply with health and safety considerations there will be no count made of used pens; only returned unused pens will be counted. In addition, subjects will be provided with a pre-printed card at each dispensing visit to record the date of each dose. The card is to be returned at the next dispensing visit with the unused pens.

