5.7. Treatment after the End of the Study

Following the final study visit subjects will be contacted by telephone 5 ± 1 weeks after last dose of study medication to assess any AEs ongoing since the last visit or newly emergent.

Subjects will be treated as deemed appropriate by the investigator following the end of the study. Investigational product will not be provided to subjects by GSK after the end of the study.

The half-life of albiglutide is approximately 5 days, and significant therapeutic concentrations can persist for 3 to 4 weeks after discontinuation. The choice of other medicinal products and dose selection should be considered accordingly, as adverse reactions may continue and efficacy may, at least partly, persist until albiglutide levels decline.

The investigator is responsible for ensuring that consideration has been given to the post-study care of the subject's medical condition whether or not GSK is providing specific post study treatment.

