8.3.6.1. Primary Analysis

The primary analysis is an ITT analysis of the time to the first occurrence of MACE over the full duration of the study. Time to event analyses will be performed using Cox's Proportional Hazard regression with SAS PHREG with treatment group as the only covariate. Data for subjects without a primary event will be censored.

Treatment differences will be estimated via the hazard ratio and its 95% confidence interval (CI).

The hypothesis of non-inferiority of albiglutide relative to placebo group with hazard ratio less than 1.3 with respect to cardiovascular risk will be tested at the end of the study. If non-inferiority is established, the hypothesis of superiority of albiglutide relative to placebo will be tested.

The absolute risk difference per 100 PY, with its associated 95% confidence interval, will also be presented.

The product-limit estimates of the probabilities (and their standard errors) of first MACE over time will be computed and displayed as Kaplan-Meier (KM) survival curves for albiglutide and placebo groups. The KM curves will also be presented corresponding to the above comparisons.

The total number of all MACE or any of its components will be analyzed by Poisson regression model. The incidence rate per 100 person-years, relative risk and their 95% CI will be presented. Number of subjects who experienced at least one event, 2 or 3 or more MACE or its components will also be summarized by treatment group.

As sensitivity analyses, the analyses described above will be repeated using events occur while on-treatment and events occur during the period of on-treatment plus 56 days post last dose.

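### The on-treatment MACE sensitivity analysis ends at the last dose date of a once-weekly drug, so it drops nearly all CV deaths on drug and nearly all events after which dosing stops

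*Protocol*

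**What the plan says.** Section 8.3.2 lists censoring dates for time-to-event data. For the on-treatment analysis it says: "For on-treatment analysis, censoring date will be the last dose date". The next line reads: "For on-therapy analysis (on-treatment+56 days), censoring date will be the last dose date+56 days". The list opens with the words "censoring time for subjects who lost to follow-up is defined as following".

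Section 8.3.6.1 names two sensitivity analyses, in which the primary MACE analyses are repeated on "events occur while on-treatment and events occur during the period of on-treatment plus 56 days post last dose". MACE is CV death, myocardial infarction or stroke, analysed as time to first event. The primary analysis is ITT.

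On exposure, section 5.1 says: "Investigational product (albiglutide or albiglutide matching placebo) will be administered once weekly by subcutaneous injection". Section 5.7 says: "The half-life of albiglutide is approximately 5 days, and significant therapeutic concentrations can persist for 3 to 4 weeks after discontinuation". Section 5.5 gives each subject a "pre-printed card at each dispensing visit to record the date of each dose", and section 4.4.1 requires the date of the last dose to be recorded at discontinuation. The last dose date is therefore the date of an actual injection, not the end of the week which that injection covers.

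**The concern.** With a weekly injection, a subject who dies while taking the drug as planned had the last injection up to 7 days before death. No later dose can exist, so the rule closes follow-up at that injection and the death falls outside it. A non-fatal infarction or stroke after which the subject never injects again is treated in the same way. In both cases the event determines the censoring date, so the censoring is informative by construction.

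The rule also conflicts with the protocol's own account of exposure. A subject four days into an ordinary dosing week counts as off treatment, although section 5.7 describes therapeutic levels lasting for weeks.

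The result would be labelled as MACE on treatment, but the hazard ratio would be close to one for non-fatal MACE followed by further dosing. Because 8.3.6.1 repeats all its analyses on this window, the Kaplan-Meier curves and the Poisson event counts are affected too. In a non-inferiority safety trial, readers look to an on-treatment analysis for harm that follow-up off drug may have diluted. This one would leave out most of the fatal component.

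**Working it through.** **Inputs from the protocol.** Dosing interval 7 days (5.1); on-treatment censoring at last dose + 0 days and on-therapy censoring at last dose + 56 days (8.3.2); half-life about 5 days (5.7); 611 events, 90% power, margin 1.3, true hazard ratio 1.0, one-sided 0.025 (8.2.1); 1:1 allocation (3.1).

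**The plan's own figure.** Events = 4 × (1.960 + 1.282)² / (ln 1.3)² = 4 × 10.507 / 0.06884 = 611. The stated 611 is reproduced.

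**Share of deaths lost.** Assume that the subject injects every week and that the time of death is unrelated to the injection day. The time from last injection to death is then uniform on 0-7 days, with mean 3.5 days. A death is kept only if it carries the same calendar date as the last injection, and only if same-day events count as events.

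- Upper bound on the share kept (injection at the start of the day): 1/7 = 14.3%, so at least 6/7 = 85.7% are lost.
- Injection at a random clock time: the share kept averages 1/2 × 1/7 = 1/14 = 7.1%, so 92.9% are lost. Simulation gave 7.15% kept.
- Injection at 20:00: 4 hours of the day remain, so (4/24)/7 = 2.4% are kept.
- With 10-20% of doses missed (assumption): about 6% kept in simulation.

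The same shares apply to non-fatal events after which no dose is taken. Non-fatal events followed by at least one more injection are kept.

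**Exposure at the time of these events.** With a 5-day half-life and simple exponential decline, the level left from the last injection is 0.5^(3.5/5) = 62% at 3.5 days and 0.5^(7/5) = 38% at 7 days. The lost events occur under substantial exposure.

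**What other windows keep (deaths in weekly users, simulation).**

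| Window | Full adherence | 10-20% missed doses |
|---|---|---|
| Last dose date, as written | at most 14%, typically 7% | about 6% |
| Last dose + 7 days | 100% | 91-81% |
| Last dose + 56 days, already planned | 100% | about 100% |

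**Illustration of the total loss.** The documents do not say what share of first MACE is fatal or ends treatment. Call that share s and take 20-40% as an assumption.

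- s = 20%, 6/7 lost: 0.20 × 6/7 = 17.1%. Of 611 on-drug events, 105 are lost and 506 remain.
- s = 40%, 13/14 lost: 0.40 × 13/14 = 37.1%. Of 611 on-drug events, 227 are lost and 384 remain.

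Power against 1.3 is Φ(½ × √events × ln 1.3 − 1.960). It gives 90% at 611 events, 84% at 506 and 73% at 384. These powers only show the loss of information. The protocol sets no power target for a sensitivity analysis, and the number of on-drug events would itself be below the ITT total.

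**The case against.** The strongest answer is that the lost events are picked up elsewhere, and that stands. The last dose + 56 days analysis sits beside this one in 8.3.6.1 and keeps practically all of them. The ITT primary analysis follows subjects after they stop the drug. CV death is analysed separately as a component of MACE (8.3.6.2). All-cause mortality has its own Cox model (8.3.6.4), censored at the date last known alive. The IDMC sees all cardiovascular event data about every 6 months (8.3.4). A reader might infer that the rule could hide a fatal hazard from the trial, or that it weakens the 611-event non-inferiority test. The documents support neither: the flaw is confined to one of two windowed sensitivity analyses, and 8.3.6.1 gives that one no priority.

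A second answer is that the list in 8.3.2 is introduced for subjects lost to follow-up, and a subject with an observed death is not lost. This does not rescue the rule. Section 8.3.2 describes the on-therapy window as on-treatment plus 56 days, and 8.3.6.1 counts the 56 days from the last dose, so on-treatment time ends at the last dose for everyone. Read literally, the lead-in would leave all other subjects with no on-treatment rule, which also needs correcting.

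A third answer is that the analysis plan, which is not at hand, may settle the detail. But the protocol does not leave the date open; it fixes one.

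It is also tempting to say that every event that ends treatment is lost. That is too absolute: events on the injection day can survive.

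**Conclusion.** The point holds as a should-fix in one sensitivity analysis. As written, the on-treatment MACE analysis drops at least 86% of CV deaths on drug, and about 93% if injection time is random. It drops the same share of non-fatal events after which dosing stops. These figures need only weekly dosing and event times unrelated to the injection day.

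The effect on the hazard ratio cannot be stated from the documents. It depends on the fatal share of first MACE, on how often a non-fatal event ends dosing, and on whether any treatment effect differs between fatal and non-fatal events. The 17-37% loss of on-drug events is an illustration under the assumed 20-40% share. A reader might call this a must-fix; the unaffected primary, mortality and +56-day analyses do not support that grading.

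**What to change.** In section 8.3.2, and in the analysis plan to match:

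- Define on-treatment time as first dose to last dose plus at least one dosing interval (7 days).
- Count events dated on or before that end date, and say so explicitly so that same-day events are settled.
- Censor subjects without an event at the earlier of that end date and the last date on which MACE status is known.
- Reword the lead-in so that the rules apply to all subjects, not only those lost to follow-up.
- Keep the +56-day analysis unchanged and state that it counts from the last dose. Its present label, on-treatment plus 56 days, would otherwise become last dose + 63 days (7 + 56).

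This changes an analysis definition only. It takes a few sentences and no new data, and should be made before unblinding. The downside is a few days of added time at risk after the last injection. Deaths after missed doses may still fall outside a 7-day window (9-19% of them with 10-20% of doses missed); the +56-day analysis covers those.

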6. STUDY ASSESSMENTS AND PROCEDURES

The schedule of study assessments is shown in [Table 1](#) and [Table 2](#). Detailed procedures for each assessment are provided in the SRM.

Table 1 Time and Events Table

| Procedures ^{1,2} | Screening ³ | Randomization ³ /Baseline (can be same day as Screening Visit) | Study Drug Check Phone Call (4-6 wks post rand.) | Clinic Visit Month 4 ± 18 days then every 4 months ± 18 days throughout the study | Unscheduled dose adjustment visit (if warranted) | Final study clinic visit ⁴ (or early withdrawal) | Follow up Phone Call 5 ± 1 weeks after last IP dose |
|--|------------------------|--|--|---|---|--|--|
| Written informed consent | X | | | | | | |
| Review of Inc/excl criteria | X | X | | | | | |
| Demography & directed medical history | X | | | | | | |
| Assessment of MACE and micro-vascular events | | | | X | | X | |
| HbA1c | X ⁵ | | | X | | X | |
| Serum creatinine (eGFR) | X ⁵ | | | X (alternate visits) ² | | X | |
| Liver Function Tests (LFTs) ⁶ | | X | | X (alternate visits) ² | | X | |
| Record available information on most recent lipid assessment ⁷ | | X | | X (annually) | | X | |
| Genetic sampling ⁸ | | X | | | | | |
| Patient reported outcomes questionnaires ⁹ | | X ¹⁰ | | X (alternate visits) ² | | X | |
| Key concomitant non-diabetes medication | | X | | X | | X | X |
| Diabetes medication | | X | | X | | X | X |
| Study drug reminder | | | X | X | X | | |
| Physical examination ¹¹ | | X | | X (alternate visits) ² | | X | |
| SAEs, AEs of special interest, AEs leading to IP discontinuation | | X | X | X | X | X | X |
| Pregnancy test ¹² | X | X | | | | | |
| Study drug dispense/compliance ¹³ | | X | | X | X | X | |

- Subjects who discontinue investigational product should be handled as described in Section 4.4 and Section 4.5 and in Table 2.
- Assessments at month 8, 16, 24 etc. will include patient reported outcomes questionnaires, serum creatinine (eGFR), LFTs and physical examination. Those at months 4, 12, 20 etc do not.
- Screening and Randomisation can occur at the same visit if all eligibility information is available. If Screening and Randomisation occur at the same visit assessments should not be duplicated.
- Once it is projected that the target number of MACE events will have been collected and that the projected median duration of subject follow-up is at least 1.5 years, a 3 month window will be defined for conducting the final, face to face visit.

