6.2.2. Adverse Events (AE) and Serious Adverse Events (SAEs)

The definitions of an AE or SAE can be found in [Appendix 5](#).

The investigator or site staff will be responsible for detecting, documenting and reporting events that meet the definition of an AE or SAE.

For this study events of myocardial infarction, stroke, unstable angina requiring urgent revascularization, hospitalization for heart failure, TIA and sudden cardiac death will not be collected or reported as AEs or SAEs. These events will be collected separately,

subjected to blinded adjudication by an independent CEC using prespecified diagnostic criteria, and reported separately (Section 6.2.1.1). All other events that meet serious criteria as defined in [Appendix 5](#) should be reported as SAEs.

All events with an outcome of death will be adjudicated to classify the cause of death as specifically cardiovascular or non-cardiovascular. Any event resulting in death should be reported as a SAE unless the event is myocardial infarction, stroke, unstable angina w/ urgent revascularization, Heart failure, TIA or sudden cardiac death which the protocol specifies are not to be collected as adverse events.

The study will not collect all non-serious AEs. Non-serious AEs leading to discontinuation of investigational product and non-serious AEs of special interest (see Section 6.2.3) will be collected.

Any events not specifically addressed above should be reported as an AE or SAE according to the definitions in [Appendix 5](#).

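### The on-therapy censoring date in Section 8.3.2 (last dose + 56 days) has no cap at last known MACE status or death, so unobserved days can count as event-free

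*Protocol*

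**What the plan says.** Protocol Section 8.3.2 lists censoring rules under the lead-in "For time to event data, censoring time for subjects who lost to follow-up is defined as following". The rule for the primary analysis is that "subjects who are lost to follow-up will be censored at the date of last evidence of confirmatory status for MACE events". The mortality rule uses the latest date on which the subject is known to be alive. The on-therapy rule reads: "For on-therapy analysis (on-treatment+56 days), censoring date will be the last dose date+56 days".

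Section 8.3.6.1 repeats the primary MACE analyses as sensitivity analyses, one of them on "events occur during the period of on-treatment plus 56 days post last dose". The analyses repeated include the absolute risk difference per 100 person-years, the Kaplan-Meier curves and the Poisson rates.

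In Table 1 the row for subjects who stay on investigational product is "Assessment of MACE and micro-vascular events | | | | X | | X". The marks fall under the 4-monthly clinic visit and the final visit, and the follow-up call has none. Section 5.7 describes that call: subjects are "contacted by telephone 5 ± 1 weeks after last dose of study medication to assess any AEs". Section 6.2.2 says that MI, stroke, heart failure hospitalisation, "TIA and sudden cardiac death will not be collected or reported as AEs or SAEs"; these events are collected separately and adjudicated.

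**The concern.** A censoring date should not lie beyond the time at which event status is known. The primary and mortality rules respect this. The on-therapy rule is a fixed offset from last dose and can run past the last observation. Days on which nobody ascertained MACE would then enter the denominators and risk sets as event-free time.

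At stake are the on-therapy incidence rates, the on-therapy risk difference per 100 person-years, the Poisson rates and the late part of the Kaplan-Meier curves. Dilution pulls absolute differences towards zero. That is an unhelpful direction in a safety trial whose Section 3.3 itself warns that missing data can favour a non-inferiority conclusion.

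**Working it through.** **The plan's own figures.** Section 8.2.1 gives 611 events for 90% power, margin 1.3, true hazard ratio 1.0 and one-sided 0.025. 4 × (1.960 + 1.282)² / (ln 1.3)² = 4 × 10.507 / 0.06884 = 610.6, so 611 is reproduced. Mean follow-up is 611/(9400 × 0.02) = 3.25 years and 611/(9400 × 0.03) = 2.17 years, against the stated 3.2 and 2.2. Nothing here disputes these figures.

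**Literal reading: subjects lost while on drug.** Section 8.2.1 plans for 1% or less lost. 9400 × 0.01 = 94 subjects, and 94 × 56/365.25 = 14.4 person-years at most. Against 9400 × 1.5 = 14,100 person-years (taking the minimum median follow-up as a mean, an assumption) that is 0.1%.

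**Broader reading: completers.**
- Dosing is weekly (Section 5.1) and no drug is dispensed at the final visit (Table 1, footnote 13). An adherent completer's last dose is therefore 0 to 7 days before that visit.
- Last dose + 56 days falls 56 − 7 = 49 to 56 − 0 = 56 days after the last scheduled MACE assessment.
- The call at 5 ± 1 weeks is on day 28 to 42, so 56 − 42 = 14 to 56 − 28 = 28 days follow it with no contact.
- Subjects who stop drug early have MACE assessed at discontinuation, at each 4-monthly contact and at the final visit (Table 2). Their 56-day window is generally observed.

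56 days is 0.153 years: 4.8% of 3.2 years, 7.0% of 2.2 years and 10.2% of 1.5 years. These bound the effect per completer. The overall effect is smaller because not everyone finishes on drug.

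**Simulation of the broader reading.** There were 3,000,000 subjects per run, with uniform accrual, exponential event times, last dose 0 to 7 days before the final visit, and no events found after that visit. Discontinuation of 10% per year in both arms is an assumption. Flat censoring at last dose + 56 days was compared with the same date capped at the final visit. The first two scenarios use Table 3 (2-year recruitment). The third is an assumed one with 1.5 years' mean planned follow-up.

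| Scenario | Event-free and on drug at end | Extra person-time | Change in rate per 100 PY (true HR 1.0) | Risk difference at true HR 1.3, capped → flat |
|---|---|---|---|---|
| 2%/yr, 4.4-yr study | 67% | +3.4% | −3.3% | 0.604 → 0.585 |
| 3%/yr, 3.2-yr study | 75% | +5.7% | −5.4% | 0.883 → 0.838 |
| 4.5%/yr, 1-yr accrual, 2-yr study | 81% | +8.6% | −7.9% | 1.354 → 1.252 |

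The rate changes follow from the person-time: 1/1.034 = 0.967, 1/1.057 = 0.946, 1/1.086 = 0.921.

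The Cox hazard ratio moved by 0.0001 or less in every run, including runs with discontinuation of 15% per year on albiglutide and 8% on placebo. With that imbalance and a true hazard ratio of 1.0, the risk difference shifted by about 0.01 to 0.02 per 100 person-years (0.008 → 0.015, 0.019 → 0.030 and −0.017 → 0.002).

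**If the call yields event status.** The mean unobserved stretch falls from 52.5 to 21 days, a factor of 21/52.5 = 0.40. The extra person-time becomes about 1.4%, 2.3% and 3.4%.

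**The case against.** The strongest objection concerns scope. The lead-in to the list names only subjects lost to follow-up, and completers are not lost. Section 8.3.6.1 says which events count; it sets no censoring date. The list therefore does not plainly say that everyone is censored at last dose + 56 days, and a reader should not infer that it does. On the literal scope the effect is negligible. What remains is that only the primary rule repeats the restriction to lost subjects and that Section 8.3.6.1 applies the window to all, so the scope is ambiguous.

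A reader might also infer that a MACE after the final visit is lost altogether. The documents do not support that. Section 6.2.2 sends such events to separate collection and adjudication, and Section 6.2.1 requires potential endpoints to be recorded whether or not the investigator suspects one. Section 6.2.2.2 prescribes open questions that could bring out an admission to hospital. An event volunteered at the call would reach the CEC. What is missing is a scheduled MACE assessment at the call and any contact from the call to day 56.

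A third inference is that subjects who die of other causes are kept at risk after death. No passage says so, and a known death is not loss to follow-up. The rule is merely silent.

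Finally, a cap can be left to the analysis plan, which is not at hand. That is partly right. But the protocol states a specific date, so under Section 8.3.6 a cap would have to be described as a deviation from it.

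**Conclusion.** The point holds as a minor fault in a stated rule. On the literal scope it adds about 14 person-years at 1% loss. On the broader scope it adds roughly 3 to 9% to on-therapy person-time and lowers the rates by about 3 to 8%, with absolute differences per 100 person-years diluted accordingly. If the call supplies event status, the inflation is about 1 to 3%. These ranges rest on assumed discontinuation rates, on adherent completers and, at the upper end, on an assumed event rate and accrual period.

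A reader might take this as a threat to the non-inferiority result. It is not. Primary inference comes from the ITT population, where censoring of lost subjects is tied to last MACE status. The on-therapy analysis is a sensitivity analysis, and its hazard ratio is essentially unchanged.

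**What to change.** In Section 8.3.2, censor subjects without an event in the on-therapy analysis at the earliest of last dose + 56 days, last confirmed MACE status and death. Apply the same cap to the per-protocol window in Section 8.3.1, which also runs to discontinuation plus 56 days. The cap works whichever way the lead-in is read. It costs one line in each section and needs no new data.

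Optionally, add the MACE assessment to the follow-up call in Table 1, and state whether events found there count in the ITT analysis. This is one more question on a call that already takes place. It would still leave 14 to 28 days of the window unobserved, so it does not replace the cap.
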